4.2. Randomization, Stratification, and Blinding

Subjects will be randomly assigned to 1 of 3 treatment groups, in a 1:1:1 ratio, as presented in [Table 3-1](#). Enrolment will be operationally managed at the study level to maintain a minimum number of subjects enrolled in 2 age groups: 6 to 10 years, inclusive; and 11 to 17 years, inclusive. Subjects will be operationally managed to maintain a minimum number of subjects enrolled in 2 age groups. A staggered enrolment is planned: the first 45 subjects enrolled will be in the older age group of 11 to 17 years, inclusive, and designated the safety lead-in cohort.

Enrolled subjects may participate in an optional substudy in which subjects may elect to participate at any time from the day of enrolment through Day 85. No randomization is planned for the substudy as all subjects participating in the open-label substudy will receive an intranasal re-vaccination/attenuated challenge with BPZE1 on Day 85.

Biostatistics will generate the randomization schedule using SAS® software Version 9.4 or later (SAS Institute Inc, Cary, North Carolina) for the interactive response technology, which will link sequential subject randomization numbers to treatment codes. The randomization schedule will

be created by the dedicated randomization team, stored in a separate project area, and will be blinded to the project team with the exception of an unblinded team who will manage vaccine logistics, preparation, and administration, but will not be involved in study-related assessments or have subject contact for data collection following study vaccination.

4.3. Analysis Set

4.3.1. Safety Analysis Set

The safety analysis set will consist of all randomized subjects who receive study vaccine and have any safety data available. Subjects will be classified according to the actual vaccine received. The safety analysis will be done on this analysis set.

4.3.2. Intent-to-Treat (ITT) Analysis Set

The intent-to-treat analysis set will consist of all randomized subjects who are vaccinated. Subjects will be classified according to the randomized treatment group. Subject disposition, demographics, and medical history will be summarized on this analysis set, and subject disposition and demographics will be summarized using the Per Protocol Immunogenicity Analysis Set as well.

4.3.3. Immunogenicity Analysis Set

The immunogenicity analysis set will consist of all subjects in the intent-to-treat analysis set who received study vaccine, have a baseline and at least 1 post-vaccination sample (mucosal or serum immunogenicity testing, respectively) for which valid results were reported for the test being analyzed, and have not received a licensed pertussis vaccine in the past 3 years or through Day 85 of the study nor received a tetanus/diphtheria vaccine through 29 days post study vaccination. Subjects will be classified according to the actual vaccine received.

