5.7 Prior and Concomitant Medications, Therapies, or Vaccines

Restrictions for prior medications, therapies, or vaccines are provided in Section 4.1.

Administration of concomitant medications, therapies, or vaccines will be recorded in the eCRF. Concomitant medications will include all medications and over-the-counter (OTC) products (including herbal supplements and multivitamins) taken by the subject from the time of signing the ICF through Day 29 (and from Day 85 [following study vaccination] through Day 113 for subjects participating in the optional substudy), or through an early termination visit, if prior to these time points. The use of anti-pyrogenic medication will be specifically queried by diary during the 7 days following any study vaccination. Concomitant medications received associated with any MAAE will be recorded through 84 days following any study vaccination; and concomitant medications received associated with any AESI or SAE will be recorded through Day 169/EOS.

Vaccines received outside of the study will be specifically queried during each visit and recorded through Day 169/EOS. Necessary vaccinations (eg, seasonal influenza, COVID-19, standard pediatric vaccines such as HPV, IPV, MenACWY) are allowed during the study, but should ideally be delayed until at least 28 days after any study vaccination whenever possible. Administration of tetanus and diphtheria toxoids (Td) vaccine during the first 90 days of the study is allowed only for emergency needs, but not as a standard schedule.

Use of new medication should prompt evaluation for the presence of a new diagnosis of chronic medical disease or condition.

6 Study Assessments and Procedures

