7.3 Analysis Sets

The safety analysis set will consist of all randomized subjects who receive study vaccine and have any safety data available. Subjects will be classified according to the actual vaccine received. The safety analysis will be done on this analysis set.

The intent-to-treat analysis set will consist of all randomized subjects. Subjects will be classified according to the randomized treatment group. Subject disposition, demographics, and medical history will be summarized on this analysis set.

The immunogenicity analysis set will consist of all subjects in the intent-to-treat analysis set who receive study vaccine, have a baseline and at least 1 post-vaccination sample (mucosal or serum immunogenicity testing, respectively) for which valid results were reported for the test being analysed, and have not received any component of a licensed pertussis vaccine in the past 3 years or through Day 85 of the study. Subjects will be classified according to the actual vaccine received. All immunogenicity analyses will be done on this analysis set. The substudy analysis set will also be based on this analysis set but including only subjects who are enrolled in the optional open-label substudy.

The per-protocol analysis set will consist of all subjects in the immunogenicity analysis set, with the following exclusions:

- Data from all available visits for subjects following the receipt of unsuitable investigational product (either via dispensed and/or assigned or delivered).
- Data from all available visits for subjects found to be ineligible at baseline per-protocol.
- Data from all available visits for subjects following the use of major immune modulators or immunosuppressants or following the receipt of blood products.
- Data from all available visits for subjects following clinically significant protocol deviations that can affect the efficacy (immunogenicity) results as determined by clinical review.
- Data from any visit that occurs substantially out of window as defined by exceeding 30 days past the visit window or the time point whereby the follow-up visit should have occurred, whichever is most restrictive. Standard visit windows are described in schedule of events (Table 13-1).

For analyses using the per-protocol analysis set, subjects will be classified according to the randomized treatment group.

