4.5. Analysis Window/Visit

Visit windows for each visit are defined in [Section 13.1](#). Additionally, analysis windows will be derived using below rules:

Study Visit/Study Day	Main Study	Substudy
Visit 1/Day 1	Day 1	
Visit S1/Day 8 ^a	Day 6 to Day 18	
Visit 2/Day 29	Day 19 to Day 57	
Visit 3/Day 85	Day 58 to Day 127	Day 58 to Day 115
SS Visit 4 ^b /Day 92	N/A	3 days before SS Visit 4 to 4 days after SS Visit 4

SS Visit 5 ^b /Day 99	N/A	3 days before SS Visit 5 to 7 days after SS Visit 5
SS Visit 6 ^b /Day 113	N/A	7 days before SS Visit 6 to 28 days after SS Visit 6
EOS/Day 169	Day 128 to Day 199	29 days after SS Visit 6 to Day 199

^a Safety Lead-in subject only

^b Subjects in substudy only

5. Subject Disposition

The number of subjects who were randomized and eligibility criteria met/failed will be summarized based on all enrolled subjects. Eligibility criteria met/failed will be listed based on all screened subjects.

Disposition of all enrolled subjects will be summarized by treatment groups, age groups (6 - 10 years, and 11 – 17 years, and 10 – 17 years) and overall including:

- Number screened
- Number screen failures
- Number of subjects randomized
- Number of subjects randomized, not vaccinated
- Number of subjects vaccinated
- Safety Analysis Set
- ITT Analysis Set
- Immunogenicity Analysis Set
- Per Protocol Immunogenicity Analysis Set
- Safety Lead-in Analysis Set
- Number of subjects who participated in substudy
- Number of subjects who completed substudy
- Number of subjects who completed study (EOS Visit)
- Number of subjects who prematurely discontinued study
- Primary reason for premature discontinuation of study

Primary reasons for study discontinuation collected on the Study Termination eCRF will be summarized with the following categories:

- Adverse Event

- Lost to Follow-Up
- Withdrawal of Consent
- Investigator Decision
- Sponsor Decision
- Death
- Other

A by subject listing will be provided based on the ITT Analysis set, subjects who are willing to participate in the substudy will also be included.

Disposition of all subjects who participate in substudy will be summarized by treatment groups, age groups (6 - 10 years, and 11 – 17 years) and overall including:

- Number of subjects who participated in substudy
- Number of subjects vaccinated on Day 1
- Number of subjects vaccinated on Day 85
- Number of subjects who are also in the following analysis sets:
 - Safety Analysis Set
 - Immunogenicity Analysis Set

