6.1. Demographics

Demographic and baseline characteristics data to be analyzed will include age, sex, race, ethnicity, weight, height, and body mass index (BMI) on the ITT Analysis set and PP Immunogenicity Analysis set by treatment group and overall, and by age group (6 - 10 years, and 11 – 17 years, and 10 – 17 years). Z-scores of height, weight, and BMI will be calculated using a SAS macro and the reference data file from the CDC website (<https://www.cdc.gov/nccdphp/dnpao/growthcharts/resources/sas.htm>)

The following characteristics will be summarized as continuous variables:

- Age (years)
- Weight (kg)
- Weight Z-score
- Height (cm)
- Height Z-score
- BMI (kg/m^2)
- BMI Z-score
- Time since last aP vaccination

Time since last aP vaccination prior to study entry will be derived based on the country's immunization schedule. The schedule is as below:

- 1) UK – 3 years old
- 2) Australia – 4 years old and 12-13 years old
- 3) Costa Rica – 4 years old

The estimated time since last aP vaccination derive method is:

- 1) UK site: estimated time since last aPV = Age -3
- 2) Costa Rica site: estimated time since last aPV = Age -4

- 3) Australia if age is ≤ 12 : estimated time since last aPV = Age -4
- 4) Australia if age is > 12 : estimated time since last aPV = Age -12

The following characteristics will be summarized as categorical variables:

- Sex (Male, Female)
- Age group (6 - 10 years, and 11 – 17 years, and 10 – 17 years)
- Race (White, Black, Asian, Pacific Islander, Aboriginal or Torres Strait Islander, Mixed or Multiple ethnic groups, Other)
- Ethnicity (Hispanic, non-Hispanic, Not reported, Unknown)
- County

A by-subject listing will be provided based on the ITT Analysis set.

6.2.Medical History

A medical history, including vaccination history, prior and concomitant medical conditions, and surgeries/significant procedures for medical conditions (eg, endoscopy, tonsillectomy), will be collected at screening and reviewed and/or updated on Day 1 if screening occurs prior to Day 1.

Medical history will be summarized based on the ITT Analysis Set and will be coded according to the latest version of Medical Drug Regulatory Activities (MedDRA). Medical history will be summarized by system organ class (SOC) and preferred term (PT), with SOCs sorted alphabetically and PTs within each SOC in descending order of frequency.

A by-subject listing will be provided for medical history based on the ITT Analysis set.

7. Treatments and Medications

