8.3.2. Analyses of Secondary Serum Immunogenicity (IgA and IgG) Endpoints

Descriptive responses (GMC [also known as GMT per protocol], GMFR, seroconversion) of IgA and IgG against WCE, PT, FHA, PRN, and any additional anti-pertussis antibodies identified during assay development will be conducted at each time point and by treatment group.

To test the hypothesis that BPZE1 and BPZE1 + Boostrix can induce significantly greater serum immunity (IgA, IgG) at Day 29 than baseline, separate paired t-tests will be used to compare the natural log-transformed GMC at Day 29 with the natural log-transformed GMC at baseline within each treatment group. The corresponding 95% CIs will be calculated on the natural log scale, then both lower and upper limits will be exponentiated to get the 95% CIs on the original scale.

A non-inferiority hypothesis will be tested to demonstrate BPZE1 + Boostrix induction of serum IgA is non-inferior to Boostrix at Day 29. An ANCOVA model that includes baseline IgA and treatment group as covariates will be used to compare the natural log-transformed GMCs at Day 29 between BPZE1+Boostrix and Boostrix groups. The non-inferiority margin is set at a 2-fold decrease or -0.693 on natural log scale. Non-inferiority will be demonstrated if the lower limit of the 95% CI of group difference on natural log scale is greater than -0.693.

To test the hypotheses that BPZE1 and BPZE1 + Boostrix can induce significantly greater serum immunity (IgA, IgG) at Day 85 and Day 169/EOS than baseline, separate paired t-tests will be used to compare the natural log-transformed GMC at Day 85 and Day 169/EOS with the natural log-transformed GMC at baseline within each treatment group. The corresponding 95% CIs by treatment group and day will be calculated on the natural log scale, then both lower and upper limits will be exponentiated to get the 95% CIs on the original scale.

The non-inferiority hypothesis will be tested to demonstrate: 1) BPZE1 induction of serum IgA and IgG is non-inferior to Boostrix at Day 85 and Day 169/EOS; 2) BPZE1+ Boostrix induction

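### Outside pertussis and Td vaccines are handled by fixed-day, whole-subject cut-offs instead of by sample date, so clean Day 29 data can be lost while boosted late serum samples are removed by no named rule

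*SAP*

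**What the plan says.** SAP 4.3.3 defines the Immunogenicity Analysis Set. Besides a baseline and a post-vaccination result, it requires that subjects "have not received a licensed pertussis vaccine in the past 3 years or through Day 85 of the study nor received a tetanus/diphtheria vaccine"; the tetanus/diphtheria limb ends 29 days after study vaccination. Protocol 7.3 has the same Day 85 rule ("have not received any component of a licensed pertussis vaccine in the past 3 years or through Day 85 of the study") and no separate tetanus/diphtheria clause.

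The PP set (SAP 4.3.4) is this set with further exclusions. SAP Section 8 runs the immunogenicity analyses on the PP set. SAP 8.1 and 8.2 use the Immunogenicity Analysis Set for the primary and key secondary sensitivity analyses.

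SAP 4.5 assigns samples from "Day 19 to Day 57" to the Day 29 visit, and main-study samples from Day 58 to Day 127 to the Day 85 visit. SAP 8.3.2 tests serum IgA and IgG against baseline at Days 29, 85 and 169/EOS. It also tests whether "BPZE1 induction of serum IgA and IgG is non-inferior to Boostrix at Day 85 and Day 169/EOS", and makes the same comparison for BPZE1 + Boostrix. The estimand table in SAP 8.1 lists no intercurrent events.

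Protocol 5.7 permits Td in the first 90 days for emergency need only, and states: "Vaccines received outside of the study will be specifically queried during each visit and recorded through Day 169/EOS".

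**The concern.** An outside vaccine affects samples taken after it and leaves earlier ones untouched. A rule that looks only at a fixed day and acts on the whole subject can therefore fail in two directions.

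- **Clean data lost.** A pertussis dose on Day 60 cannot have affected a sample drawn on Day 29, yet the subject leaves both analysis sets and no planned analysis recovers the result. Membership of the primary analysis set is also unsettled at an interim lock that requires only Day 29 to be complete.
- **Affected data kept.** A pertussis dose on Day 100 can raise the Day 169 serum titres, yet no named rule removes that sample.

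At stake are the late serum tests against baseline and for non-inferiority and, to a small extent, primary power. The SAP's own schedule ("Australia – 4 years old and 12-13 years old") puts a routine booster inside the 6 to 17 year enrolment range.

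**Working it through.** **1. Calendar check** (Day 1 is vaccination; visit allowances from the schedule of events; analysis windows from SAP 4.5).

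- Pertussis cut-off: Day 85, so the first dose not covered is on Day 86.
- Main-study Day 85 visit: 85 + 14 = Day 99. Its analysis window ends on Day 127. The PP lateness rule, read strictly, ends it at 85 + 30 = Day 115. A Day 86 dose can thus precede a retained sample by 99 − 86 = 13 days within the visit window, 29 days to Day 115, or 41 days to Day 127.
- Day 169/EOS: a Day 86 dose precedes it by 169 − 86 = 83 days, or 113 days if the visit falls on Day 199.
- In the other direction, a dose in the 56 days between a Day 29 sample and Day 85 removes that sample.
- Td cut-off: 1 + 29 = Day 30. The Day 29 sample may be drawn to 29 + 7 = Day 36 and is analysed to Day 57. A Day 31 dose can precede it by 5 or 26 days.

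**2. Cost of losing Day 29 data.** The plan states 95% power per primary comparison (N = 108, effect size 0.35, two-sided 0.05) and 90% jointly. Paired t-test power from the noncentral t distribution (107 df, noncentrality 0.35 × √108 = 3.64) gives 95.0%, and 0.950² = 90.2%, so the plan's figures are reproduced. The loss rates below are assumed.

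| Subjects lost | n | Power per group | Joint power |
|---|---|---|---|
| 1% | 107 | 94.8% | 89.9% |
| 3% | 105 | 94.4% | 89.2% |
| 5% | 103 | 94.0% | 88.4% |
| 10% | 97 | 92.7% | 85.9% |

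**3. Effect of keeping boosted samples.** If a fraction f of an arm has an R-fold rise, the arm's mean log titre shifts by f × ln R and its geometric mean is multiplied by exp(f × ln R). Both f and R are assumed. For R = 10 (ln R = 2.303):

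| f | Log shift | Geometric mean | Share of 0.693 |
|---|---|---|---|
| 1% | 0.023 | × 1.023 | 3.3% |
| 3% | 0.069 | × 1.072 | 10.0% |
| 5% | 0.115 | × 1.122 | 16.6% |

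At f = 5%, R from 4 to 20 gives shifts of 0.069 to 0.150, or 10 to 22% of the margin.

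**4. Worst case for the non-inferiority test.** Put every booster in the BPZE1 arm, set the true ratio exactly at 0.5, and take n = 108 per arm and the planning SD for PT (0.8759, SAP Table 4-2). The nominal one-sided error of 0.025 becomes 0.042 to 0.072 at f = 2% and 0.084 to 0.239 at f = 5%, for R from 4 to 20. Boosting also widens the boosted arm's SD, to √(0.8759² + f(1 − f)(ln R)²). Allowing for that, f = 5% and R = 10 gives 0.143 instead of 0.159. These figures are illustrative: the SD is a planning value for Day 29, and the SAP uses ANCOVA adjusted for baseline.

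**The case against.** **The PP set could already catch these samples.** A reader might infer that an outside pertussis dose after Day 85 is excluded nowhere. That goes too far. SAP 4.3.4 drops visits following clinically significant deviations that can affect immunogenicity, decided blinded before lock. Protocol 5.7 names no pertussis-containing vaccine among its examples of allowed vaccines, and the information card is meant to prevent such doses throughout the study. An outside Tdap is a natural candidate for that bullet. What remains is that removal is discretionary, no text declares such a dose a deviation, the Immunogenicity Analysis Set has no such bullet, and the bullet cannot restore lost Day 29 data. Emergency Td is permitted, so it is not in itself a deviation.

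**The substudy is protected before the challenge.** Its Day 85 visit may run to Day 105, which looks like another route for boosted samples. It is closed: protocol 4.1.2.1 excludes anyone given an outside pertussis vaccine since enrolment, and eligibility is checked again before the challenge.

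**The direction is not fixed.** A reader might infer that contamination always favours the sponsor's claim. It does in tests of a BPZE1 arm against baseline, and in non-inferiority tests when boosters fall mainly in a BPZE1 arm. Boosters in the Boostrix arm work against non-inferiority. Subjects are blinded, so nothing in the documents places the boosters in one arm. Nor is mucosal durability clearly exposed: the protocol's background reports that Boostrix did not induce S-IgA in adults.

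**The Td gap is narrow.** The endpoint is the proportion at or above 0.1 IU/mL, both arms compared receive Boostrix, and planning assumes at least 95% above the threshold. A late Td dose could change only the few still below it. This stands.

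**The clause might seem to catch study Boostrix as well.** That is not a credible reading, because it would empty two of the three arms and abolish the key secondary comparison.

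**Conclusion.** The point holds in a bounded form. The cut-offs are tied to fixed days and whole subjects, so by rule they discard clean Day 29 results after a pertussis dose given by Day 85. They also name no exclusion for serum samples taken after a dose given later than Day 85.

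The loss of primary power is minor: about half a percentage point per comparison at 3% loss. The larger exposure is in the non-key secondary serum tests at Day 85 and Day 169/EOS. There, 1 to 5% boosting of one BPZE1 arm at 10-fold would raise its geometric mean by about 2 to 12%. The Td gap is of the same kind and probably negligible for its endpoint.

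The calendar findings rest on the documents alone. The sizes rest on assumed rates and fold rises, because the documents give no frequency of outside vaccination and no number of Australian subjects. The information card should keep the rate low. The change is worth making because the rule is simple to correct before lock.

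**What to change.** In SAP 4.3.3, and in protocol 7.3 if it is amended, keep the 3-year pre-study condition and replace the on-study clause with a per-sample rule through Day 169/EOS:

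- Exclude data from samples collected after a pertussis-containing vaccine received outside the study; retain earlier data.
- For tetanus and diphtheria endpoints, exclude data from samples collected after any outside tetanus/diphtheria-containing vaccine; retain earlier data.

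Apply this in both the Immunogenicity and PP sets, and list outside vaccination as an intercurrent event in the SAP 8.1 estimand table.

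The cost is SAP wording and one programming condition comparing sample date with dose date. Outside vaccines are already recorded through Day 169/EOS, and the existing cut-offs already need the dose date. The PP set already uses the same form of rule for data following immune modulators or blood products.

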4.3.4. Per-Protocol (PP) Immunogenicity Analysis Set

Immunogenicity Analyses to be performed based on PP Immunogenicity Analysis Set.

The PP immunogenicity analysis set will consist of all subjects in the immunogenicity analysis set, with the following exclusions:

- Data from all available visits for subjects following the receipt of unsuitable investigational product (either via dispensed and/or assigned or delivered).
- Data from all available visits for subjects found to be ineligible at baseline per protocol.
- Data from all subjects who received at least one dose of whole-cell pertussis (wP) containing vaccine in their life.
- Data from all available visits for subjects following the use of major immune modulators or immunosuppressants or following the receipt of blood products.
- Data from all available visits for subjects following clinically significant protocol deviations that can affect the efficacy (immunogenicity) results as determined by clinical review.

- Data from any visit that occurs substantially out of window as defined by exceeding 30 days past the visit window or the time point whereby the follow-up visit should have occurred, whichever is most restrictive.
- For subjects in the colonization substudy, missing Day 92 and Day 99 cultures will be removed from the Colonization endpoint.

For analyses using the PP immunogenicity analysis set, subjects will be classified according to the randomized treatment group. Determination of exclusions from the PP Immunogenicity Analysis Set will be performed by the sponsor clinical lead in a blinded fashion prior to the database lock.

